1 PROTOCOL SUMMARY

1.1 SYNOPSIS

Title:	The Effects of an LED Face Mask & Neck and Chest Mask On Skin Health
Study Type:	Single Group, Virtual
Product(s) being tested	The iRESTORE Illumina LED Face Mask and The iRESTORE Illumina LED Neck & Chest Mask
Study Intervention Description:	
This single-group study will involve 38 participants for a total of 12 weeks.
 
Participants will use the test products once daily for 10 minutes in the evening while getting ready for bed.
 
Participants will use Mode 1 only for all sessions of the face mask - the neck and chest mask does not have multiple settings.
 
Participants will complete questionnaires at Baseline, Week 2, Week 4, Week 6, Week 8, Week 10, and Week 12.
 
Participants will also provide photos of their faces at Baseline and Week 12 for dermatologist skin grading.
 
Participants will utilize the test products at home and complete questionnaires online.

Objectives:	
Primary Objective: To examine the effectiveness of the iRESTORE Illumina LED Face Mask and The iRESTORE Illumina LED Neck & Chest Mask in improving skin health outcomes.
 
Secondary Objective: To assess changes in participant perception of skin health.

Endpoints:	
Primary Endpoint: Improvements in skin health parameters will be evaluated by dermatologist grading at Baseline and Week 12.
 
Secondary Endpoint: Participant perceptions of skin health, including plumpness, fine lines and wrinkles, appearance of pigmentation, skin tone and texture, skin redness, firmness, and radiance, and the appearance of crepey skin will be evaluated through subject-specific questionnaires at Baseline, Week 2, Week 4, Week 6, Week 8, Week 10, and Week 12.

Study population	38 female participants aged 25-55
Study Duration:	12 weeks
Description of Sites/Facilities Enrolling Participants:	Virtual

Survey Milestones	Baseline, Week 2, Week 4, Week 6, Week 8, Week 10, and Week 12.
Photo Milestones	Baseline and Week 12
	
Participants will use the iRESTORE Illumina LED Face Mask and The iRESTORE Illumina LED Neck & Chest Mask for 10 minutes once daily while getting ready for bed.
 
Participants will use Mode 1 only for all sessions of the face mask. The neck and chest masks do not have multiple settings. Full instructions will also be written in the manual included with the kit.
 
iRESTORE Illumina LED Face Mask
 
Set Up
 
Connect the power cord to the mask. Attach the two parts of the upper strap to the mask (labeled UL for Upper Left and UR for Upper Right). If desired, attach the lower straps as well (labeled LL for Lower Left and LR for Lower Right). The lower straps are optional and are designed to allow the user to pull the mask closer to the face.
 
Preparation
 
Cleanse your face to remove all makeup, skincare, dirt, and oils. Place the mask comfortably on your face and lightly tighten the straps. Ensure the mask is snug but not too tight. Adjust the upper straps upward to relieve pressure.

Directions For Use:	
Step 1 Press and hold (Power) button to turn on the mask. The mask enters P1 mode automatically.
 
Step 2 Once a mode is selected, press (Start/Pause) button to begin a 10-minute session, and the indicator light will turn on. Once the session is complete, the indicator light will turn off, and the mask will turn off automatically in 30 seconds. Note: If the (Start/Pause) button is not pressed within 30 seconds once a mode is selected, the mask will turn off automatically.
 
Step 3 If you need to pause the session at any time, press the (Start/Pause) button, and the indicator light will flash. Press the (Start/Pause) button to resume the session, and the indicator light will turn on. If the (Start/Pause) button is not pressed within 30 seconds during a paused session, the mask will turn off automatically.
 
Step 4

	
Hold the (Power) button for several seconds if you need to turn off the mask. The indicator light will turn off immediately; then, the mask will turn off in 30 seconds.
 
iRESTORE Illumina LED Neck & Chest Mask
 
Neck & Chest Mask
 
Set Up
 
Connect the power cord to the mask. For a full neck and chest treatment, attach the lower straps (labeled LL for Lower Left and LR for Lower Right) to the two ends of the mask. If you want to focus on treating the chest only, remove the lower straps and attach the upper straps (labeled UL for Upper Left and UR for Upper Right) to the holes at the top of the mask, then let it hang from your neck.
 
Preparation
 
Position the mask on your chest and around your neck, and lightly tighten the strap. Ensure the mask is snug but not too tight to cause discomfort.
 
Step 1 Press and hold the power button to turn on the mask.
 
Step 2 Press the (Start/Pause) button to begin a 10-minute session; the indicator light will turn on. After the session, the mask will automatically turn off in 30 seconds. Note: If you don't press the (Start/Pause) button within 30 seconds, the mask will shut off automatically.
 
Step 3 If you want to pause the session at any time, press the (Start/Pause) button, and the indicator light will flash. Press the (start/pause) button to resume the session, and the indicator light will turn on. If the (Start/Pause) button is not pressed within 30 seconds during a paused session, the mask will turn off automatically.
 
Step 4 Hold the (Power) button for several seconds if you need to turn off the mask. The indicator light will turn off immediately; then, the mask will turn off in 30 seconds.

Compensation	\$125 Visa gift card
Devices	Phone/Digital Camera (participants must provide) iRESTORE Illumina LED Face Mask (sponsor provides) iRESTORE Illumina LED Neck & Chest Mask (sponsor provides)

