1.2 SCHEMA

Prior to enrollment:

Total N=38. Obtain informed consent. Screen potential participants by inclusion and exclusion criteria. Participants complete a Baseline questionnaire and take Baseline photos of their face, neck, and chest (decollage area).

Intervention:

Intervention Information

Study Period = 12 weeks

Participants will use the face mask and neck and chest masks for 10 minutes daily, while getting ready for bed.

For the face mask, mode 1 should be used for all sessions. The neck and chest mask does not have multiple settings.

Questionnaires will be completed at Baseline, Week 2, Week 4, Week 6, Week 8, Week 10, and Week 12.

Photos will be taken at Baseline and Week 12 for expert skin grading.

Final Assessments

Statistical analysis performed

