3 OBJECTIVES AND ENDPOINTS

OBJECTIVES	ENDPOINTS	TIMEPOINTS	ASSESSED BY	JUSTIFICATION FOR ENDPOINTS
Primary Objective : To evaluate changes in overall skin appearance, as measured by dermatologist skin grading.	Improvement in Skin Appearance	Baseline and Week 12	Photographs via Dermatologist Skin Grading	Standardized photographs provide objective data on the changes in skin appearance, specifically targeting wrinkles, fine lines, and other signs of aging.

Secondary Objectives: To assess changes in a range of skin health parameters.	Improvement in skin plumpness, fine lines and wrinkles, pigmentation, tone and texture, redness, firmness, elasticity, radiance, and appearance of crepey skin.	Baseline, Week 2, Week 4, Week 6, Week 8, Week 12	Questionnaires	Self-reported questionnaires provide subjective data on perceived changes in wrinkles and fine lines.
--	---	---	----------------	---

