4 STUDY DESIGN

4.1 OVERALL DESIGN

This 12-week single-group, virtual clinical study is designed to evaluate the efficacy of the iRESTORE Illumina LED Face Mask and The iRESTORE Illumina LED Neck & Chest Mask. The study will involve 38 participants, aged between 25 and 55 years, with self-reported skin issues, who will use the devices once daily for 10 minutes daily for 12 weeks.

Data collection will include questionnaires at Baseline, Week 2, Week 4, Week 6, Week 8, Week 10, and Week 12. In addition, participants will provide photos at Baseline and Week 12 to assess changes in skin health and appearance.

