6.3 RANDOMIZATION AND BLINDING

There will be no randomization or blinding in this trial.

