7 STATISTICAL CONSIDERATIONS

Following data collection and the completion of the trial, the data will be analyzed by Citruslabs to determine the effect of the intervention. Repeated-measure, between time points, statistical tests will be used to examine changes in primary and secondary endpoints versus the Baseline.

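### The protocol does not say when the primary-endpoint photos are graded or by whom, so it permits separate Baseline and Week 12 readings whose difference in grading standard would count as skin change.

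*Combined protocol and SAP*

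**What the plan says.** The Synopsis states the primary endpoint as follows: "Improvements in skin health parameters will be evaluated by dermatologist grading at Baseline and Week 12". The table in Section 3 gives the same two time points and names the assessment as "Photographs via Dermatologist Skin Grading". Its justification is that "Standardized photographs provide objective data on the changes in skin appearance".

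The Schema (Section 1.2) ties the two times to photography: "Photos will be taken at Baseline and Week 12 for expert skin grading". Sections 4.1, 6.1 and 6.5 do the same. The Schedule of Activities (Section 1.3) has a row for photos and none for grading. Section 6.5 controls how photos are taken (light, pose, no makeup or filter), not how they are graded.

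Section 6.3 reads: "There will be no randomization or blinding in this trial". It does not separate participants from graders. The analysis in Section 7 is one sentence: "Repeated-measure, between time points, statistical tests will be used to examine changes in primary and secondary endpoints versus the Baseline". It has no term for grader or reading session.

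No section gives the reading time, the number of dermatologists, the assignment of images to graders, the order of presentation or the grading scale.

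**The concern.** A grade read from a photo is a human judgement, and its standard can move. One grader may become more lenient or stricter between two sittings, and two dermatologists may apply different standards. In a controlled trial, a shift common to both arms cancels in the comparison between arms. Here Section 4.1 describes a "This 12-week single-group, virtual clinical study is designed to evaluate the efficacy" of the devices in one group, and the primary result is the within-person change. If the Baseline images are read in one batch and the Week 12 images in a later one, or if the grader follows the visit, the shift and the skin change cannot be told apart from the grades.

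This is separate from a grader knowing which visit a photo shows. A grader unaware of the time point can still drift between two batches. A grader who reads both images in one sitting but knows which is later remains open to expectation. The reading procedure has to deal with both.

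**Working it through.** **Inputs from the documents.** N = 38 (Synopsis, Sections 4.1 and 5.4); one group; two graded time points; change from Baseline. Section 5.4 gives no significance level, power, effect size, SD or dropout, so the figure of 38 cannot be reproduced.

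**Assumptions, none of them in the documents.** Two-sided 5% paired t-test; all 38 participants graded at both times; true skin change of zero; a common grading shift d toward improvement, in SDs of the paired change.

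**Step 1, what the estimate contains.** Let g0 and g1 be the grading standards in force when the Baseline and Week 12 images are read, and Δ the true change. The mean paired change estimates Δ + (g1 − g0). If both images are read to one standard, g1 − g0 = 0. If the readings are separate, the term stays, and there is no second arm from which to subtract it.

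**Step 2, false significant improvement when Δ = 0.** With 37 degrees of freedom the critical value is t = 2.026. The noncentrality is d√38 = 6.164d. The probability is 1 − F(2.026; 37, 6.164d), where F is the noncentral t distribution function.

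| Shift d (SD) | Noncentrality | n = 38 | Normal approximation, n = 38 | n = 30 (assumed completers) |
|---|---|---|---|---|
| 0 | 0 | 2.5% | 2.5% | 2.5% |
| 0.1 | 0.62 | 8.7% | 9.0% | 7.6% |
| 0.2 | 1.23 | 22.4% | 23.4% | 18.4% |
| 0.3 | 1.85 | 43.7% | 45.6% | 35.5% |
| 0.5 | 3.08 | 85.1% | 86.9% | 75.4% |

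A shift of the same size toward worse grades lowers the chance of a false improvement at n = 38 (0.5% at 0.1 SD, 0.1% at 0.2 SD) and subtracts from any true benefit.

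**Step 3, how large a shift matters.** The smallest observed mean change that reaches p < 0.05 is 2.026 / 6.164 = 0.33 SD. A true change of about 0.47 SD gives 80% power. A shift of 0.2 to 0.3 SD is therefore a substantial part of what this study could detect.

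**Step 4, a different dermatologist at each time point.** Let grader leniency vary with SD τ, in units of the SD of change, so that g1 − g0 has SD τ√2. In 40,000 simulated trials with no true change, the two-sided false-positive rate was about 13%, 32%, 47% and 65% for τ = 0.1, 0.2, 0.3 and 0.5. About half of these were toward improvement. With the offset removed, as when the same grader reads both images to one standard, the rate was 4.9% to 5.1%.

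**The case against.** The strongest reply is that the two times in the endpoint sentence name the visits being compared, not the dates of grading. The Schema and Sections 4.1, 6.1 and 6.5 attach those times to taking photos. Section 3 lists them as time points and puts grading in a separate column. Section 7 places the analysis after data collection, which fits a single reading at the end. This stands. A reader might infer that the protocol fixes the two gradings 12 weeks apart. The documents do not support that; they leave the reading time open.

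A reader might also infer that reading session and grader are fully confounded with time. That holds only if the reading batch or the grader follows the visit, and the documents state neither. No section mentions a second dermatologist, and graders mixed across both time points would mainly add noise. Enrolment may also be staggered, so that Baseline and Week 12 readings overlap in calendar time. That helps only in part: if photos are graded as they arrive, each participant's two readings are still about 12 weeks apart, and a steady drift enters every pair.

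The percentages are the power curve of a paired t-test with drift in place of effect. Apart from N = 38 they carry no information about this trial. This also stands, and they are offered only to show scale.

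Finally, the harm is not beyond repair. The existing grades cannot be corrected by analysis, but photos that have been kept can be read again in one session. That supports choosing the better reading at the outset.

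**Conclusion.** The point holds in conditional form. The protocol leaves reading time and grader assignment for its only primary endpoint unstated, rules out blinding without exempting the grader, and uses wording that permits separate readings. If the readings are separate, any shift in grading standard goes directly into the estimated improvement, upward or downward.

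Its size is unknown. Under the assumptions listed, shifts toward improvement of 0.1 to 0.5 SD raise the chance of a false significant improvement from 2.5% to between about 9% and 85%. The documents give no scale, SD or grader reliability with which to judge what shift is plausible. They do not show that drift will occur, or that it would favour the devices. The change is worth making because a pooled, masked reading of stored photos is less open to bias and costs very little.

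**What to change.** In the Synopsis and Section 3, say that photos are taken at Baseline and Week 12 and that all of them are graded after the last Week 12 photo has been received, in one reading period. State that both time points of a participant are graded by the same dermatologist on the same scale, and name that scale, since none is given. If more than one dermatologist is used, keep each participant's images with one of them. Present images in random, intermixed order, masked to time point. In Section 6.3, state that the grader is masked to time point although participants are not blinded.

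The cost is that Baseline grades are not available early and that images must be coded and shuffled before reading. No extra participants, images or staff are needed, and N stays at 38. The change must be in place before any grading starts.

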1.2 SCHEMA

Prior to enrollment:

Total N=38. Obtain informed consent. Screen potential participants by inclusion and exclusion criteria. Participants complete a Baseline questionnaire and take Baseline photos of their face, neck, and chest (decollage area).

Intervention:

Intervention Information

Study Period = 12 weeks

Participants will use the face mask and neck and chest masks for 10 minutes daily, while getting ready for bed.

For the face mask, mode 1 should be used for all sessions. The neck and chest mask does not have multiple settings.

Questionnaires will be completed at Baseline, Week 2, Week 4, Week 6, Week 8, Week 10, and Week 12.

Photos will be taken at Baseline and Week 12 for expert skin grading.

Final Assessments

Statistical analysis performed

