1.3 SCHEDULE OF ACTIVITIES (SoA)

Procedures	Screening	Intervention	Conclusion
Informed Consent	X		
Demographics	X		
Inclusion/ Exclusion	X		
Administer Study Intervention		X	
Surveys	X	X	X
Photos	X		X
Adverse Event Review and Evaluation	X	X	X

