5 STUDY POPULATION

5.1 INCLUSION CRITERIA

To be eligible to participate in this study, an individual must meet all of the following criteria:

- Female
- Aged 25-55 years.
- Willing to follow the study protocols.
- Self-reported issues with at least two of the following:
 - Fine lines
 - Wrinkles
 - Hyperpigmentation
 - Dark spots
 - Reduced elasticity
- Self-report concerns with at least one of the following:
 - Crepey skin on the neck and chest
 - Sun damage on neck and chest
- Willing to avoid introducing any new products, prescription medications, or supplements that target skin health during the study period.
- If taking oral supplements or herbal remedies targeted at skin health and appearance, have been consistently taking these for at least 3 months prior to starting the study.
- Is willing to maintain the routine of any oral supplements or herbal remedies targeted at skin health and appearance for the duration of the study.
- Has been using the same skincare routine for at least one month prior to the study start date.
- Willing to maintain the same skincare routine and products throughout the study.
- Willing to avoid direct sun exposure during the study duration
- Willing to wear sunscreen if have to be in the sun

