5.2 EXCLUSION CRITERIA

An individual who meets the following criteria will be excluded from participation in this study:

- Anyone who is extremely satisfied with their skin.
- Anyone who has any chronic health conditions such as oncological (cancer) or psychiatric disorders.
- Anyone who is planning to undergo facial treatments during the study period, including botox, dermal filler, chemical peels, etc. or has experienced any of these treatments in the last 3 months.

- Anyone diagnosed with a skin condition affecting the face and/or neck who has had an active flare-up or breakout within the last year. This includes but is not limited to acne, eczema, psoriasis, rosacea, seborrheic dermatitis, vitiligo, urticaria (hives), warts, atopic dermatitis, melasma, and contact dermatitis.
- Currently using any prescription medications that may affect the skin condition including but not limited to the following:
 - Corticosteroids like prednisone, methylprednisolone
 - Antipsychotics like olanzapine (Zyprexa), risperidone (Risperdal), quetiapine (Seroquel)
 - SSRIs and SNRIs like fluoxetine (Prozac), sertraline (Zoloft), venlafaxine (Effexor)
 - Anticonvulsants like phenytoin (Dilantin), lamotrigine (Lamictal), and carbamazepine (Tegretol)
 - Antihypertensives like lisinopril (Zestril), amlodipine (Norvasc), and propranolol (Inderal)
 - Antithyroid medications like Tapazole (methimazole), Propyl-Thyacil (propylthiouracil)
- Anyone with a history of skin cancer or precancerous skin lesions on the face.
- Anyone who has any known serious allergic reactions that require the use of an Epi-Pen.
- Anyone who has any known allergies to ingredients commonly found in skincare products.
- Anyone who is pregnant, breastfeeding, or trying to conceive
- Anyone who cannot/will not commit to the study protocol.
- Anyone with a history of substance abuse.
- Anyone who has undergone an invasive medical procedure in the three weeks prior to the study or has a procedure planned during the study duration.
- Anyone with a known allergic reaction to aluminum or plastics.
- Anyone who suffers from any photosensitive disorder (sensitization to light).
- Anyone with uncontrolled acne.
- Anyone taking any prescription medication, over-the-counter supplements, or herbal supplements regularly (three or more days per week) that can cause photosensitivity including but not limited to the following:

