5.4 JUSTIFICATION OF SAMPLE SIZE

A sample size of 38 participants provides a balance between obtaining statistically significant results and maintaining a manageable cohort for detailed analysis and follow-up.

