6 STUDY INTERVENTION

6.1 STUDY INTERVENTION

- Participants will be sent one iRESTORE Illumina LED Face Mask and one iRESTORE Illumina LED Neck & Chest Mask.
- Participants will use both products for 10 minutes daily in the evening. For the face mask, Mode 1 should be used for all sessions. The neck and chest mask does not have multiple settings.
- Questionnaires will be completed at Baseline, Week 2, Week 4, Week 6, Week 8, Week 10, and Week 12.
- Photos will be taken at Baseline and Week 12.

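### The analysed Baseline is taken at screening, before enrollment, and is not tied to first device use; this could inflate self-reported improvement and lets pre-use change into the 12-week comparison

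*Combined protocol and SAP*

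**What the plan says.** Section 1.2 opens with a block headed "Prior to enrollment". After consent and the eligibility screen, that block reads: "Participants complete a Baseline questionnaire and take Baseline photos of their face, neck, and chest". The schedule in Section 1.3 matches it. The first surveys and photos share the Screening column with the eligibility check, and device use starts only in the Intervention column. No days or windows are given.

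Eligibility rests on self-report. Section 5.1 asks for "Self-reported issues with at least two of the following" (five face items) and a concern with at least one of two neck and chest items. Section 5.2 excludes "Anyone who is extremely satisfied with their skin".

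Section 6.1 says: "Participants will be sent one iRESTORE Illumina LED Face Mask and one iRESTORE Illumina LED Neck & Chest Mask". It gives no dispatch, receipt or first-use date. Section 6.4 provides for people who consent but never receive the intervention, so the plan itself expects a gap between consent and receipt. Section 5.1 counts the one-month stable skincare routine back from a study start date that is not defined.

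Section 6.3 states that there is no randomization or blinding, and the design has a single group. Section 7 tests primary and secondary endpoints as change from Baseline.

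**The concern.** People admitted because they report skin problems will include some who were reporting worse than their usual level that day. If the analysed Baseline is collected in the same step, part of that transient error can carry into it and fade by later surveys without any treatment. The secondary endpoints are self-reports on overlapping attributes (fine lines and wrinkles, pigmentation, crepey skin), and one Baseline serves all six later surveys. No control arm is available to subtract the effect.

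A second route does not depend on selection. With no window from Baseline to first use, an unknown period without treatment falls inside the before-after comparison. Participants take the photos in natural light, and Section 6.5 asks for the same place, time and lighting only where possible. Any change in skin or light over that period is counted in the 12-week change of the dermatologist-graded primary endpoint as well as the self-reports.

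**Working it through.** **The plan's own figure.** Section 5.4 says only: "A sample size of 38 participants provides a balance between obtaining statistically significant results". It gives no effect size, SD, alpha, power or dropout, so 38 cannot be reproduced. What follows is an illustration on stated assumptions.

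**From the documents:** n = 38, single group, change from Baseline.

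**Assumed:** a two-sided 5% paired t-test, normal scores and no device effect. Also assumed are test-retest correlation ρ, share of applicants qualifying p, and c, the correlation between transient error in the screening self-report and in the Baseline score. With c = 1, Baseline is itself the selecting score. With c = 0, it shares no transient error with screening.

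**Formulas.**
- Selection intensity: i(p) = φ(z)/p, where z cuts off the top fraction p. i(0.5) = 0.798, i(0.7) = 0.497, i(0.9) = 0.195.
- Expected fall, in SD of one measurement: c(1−ρ)i(p).
- Standardized change: dz = fall / √(2(1−ρ)).
- Chance of a significant improvement: upper tail of the noncentral t with 37 df and noncentrality dz√38, beyond 2.026.

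**Example** (ρ = 0.7, p = 0.5, c = 0.5): fall = 0.5 × 0.3 × 0.798 = 0.120 SD; dz = 0.120/0.775 = 0.155; noncentrality = 0.155 × 6.164 ≈ 0.95; chance = 15%.

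| ρ | p | Fall, c=0.5 | Chance, c=0.5 | Fall, c=1 | Chance, c=1 |
|---|---|---|---|---|---|
| 0.7 | 0.5 | 0.120 | 15% | 0.239 | 46% |
| 0.7 | 0.7 | 0.075 | 8% | 0.149 | 21% |
| 0.7 | 0.9 | 0.029 | 4% | 0.058 | 7% |
| 0.8 | 0.5 | 0.080 | 11% | 0.160 | 33% |
| 0.8 | 0.7 | 0.050 | 7% | 0.099 | 15% |
| 0.8 | 0.9 | 0.019 | 4% | 0.039 | 6% |

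At c = 0 the chance is the nominal 2.5%. Simulation agrees at c = 0.5. At c = 1 it gives 49% in the top row, because selection also shrinks the SD of change (0.731 against 0.775). Rounded outward, the c = 1 range is about 5% to 50%.

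**Wider assumptions.** ρ = 0.9, p = 0.8, c = 0.5 gives 0.02 SD and 4%. ρ = 0.5, p = 0.3, c = 1 gives 0.58 SD and 94%.

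**The actual entry rule.** I simulated two of five face items plus one of two neck and chest items, with the screening answers taken as cut-offs of the Baseline scores. I assumed ρ = 0.7, true-score correlation between items of 0.4 and transient-error correlation of 0 to 0.4.

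| Share qualifying | Listed face item | Neck or chest item | Outcome not on the entry list |
|---|---|---|---|
| 70% | 4% to 10% | 6% to 13% | 3% to 9% |
| 50% | 5% to 21% | 9% to 27% | 2% to 16% |

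The comparable c = 1 figures in the first table are 21% and 46%.

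**Drift before first use, no selection.** A shift of 0.1 SD gives two-sided rejection of 9%, 12% or 27% at ρ = 0.5, 0.7 or 0.9. A shift of 0.2 SD gives 22%, 34% or 77%. The sign may favour the devices or go against them. For scale, n = 38 has 80% power at dz = 0.47.

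**The case against.** A reader might infer that the Baseline questionnaire is the score that admits people, so that the upper range applies. The documents do not say that. Eligibility is a yes/no self-report with no severity cut-off, and Section 1.2 lists screening and the questionnaire as successive steps. A single Screening column shows that both precede device use, not that they share a sitting. Several questionnaire attributes, such as plumpness, redness and radiance, are not on the entry list. This stands, and it makes the c = 1 column an upper bound for a given correlation and qualifying share.

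A reader might also infer that the primary endpoint is inflated by regression to the mean. The primary is a dermatologist's grade of photographs, which is not the selection variable, so little of that effect should reach it. The exposure there is mainly pre-use change.

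Nor do the documents support reading drift as a bias toward the devices, because it can go either way. Section 5.1 already limits it through stable skincare and supplement routines and no new skin products, and Section 6.5 asks for consistent photo conditions where possible.

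Finally, the root problem is the missing control arm, and having the kit in hand before Baseline creates a chance of early use. Both are fair. Neither is a reason to keep a Baseline that adds avoidable error within the chosen design. The second is met by requiring the measures before any use and recording the first-use date.

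**Conclusion.** The point holds in a limited form. The documents place the analysed Baseline before enrollment, in the screening step, with no link to first use. Regression to the mean could therefore inflate the self-reported secondary endpoints, and change before first use would be counted in both endpoints with unknown sign. The bias is possible, not shown to be present.

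Its size depends on assumed values that the documents do not supply. With ρ of 0.7 to 0.8 and 50% to 90% qualifying, the chance of a false significant improvement per self-reported attribute is about 4% to 15% at c = 0.5, with an upper bound of about 5% to 50% at c = 1, against 2.5% nominal. Outside those ranges the effect runs from negligible to dominant.

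This is a stated timing that can be changed cheaply, so it is worth correcting before recruitment.

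**What to change.** - Keep the eligibility self-report at screening.
- Take the analysed Baseline questionnaire and photos after eligibility is confirmed and the kit has arrived, within a few days before the first session and before any use.
- Record the first-use date and count Weeks 2 to 12 from it.
- Update Sections 1.2 and 1.3 to match.

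The cost is a timing change in a remote study, with no extra visit. Some kits will go to people who never start. Section 6.4 allows replacement of those who did not receive the intervention and rules it out for those who received it and then left. It should say whether people who hold a kit but never start may be replaced.

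The change removes pre-use drift and moves c toward 0. Expectation, season and the sun avoidance asked for in Section 5.1 still act after first use with no control arm, so the report should say that the remaining change cannot be attributed to the devices.
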